2.4. Follow-up

Following the Safety Follow-up Visit / End of Core Study Visit, subjects will be followed up with an Efficacy and Survival follow-up for response duration and survival every 3 months for 12 months (in Part A) and every 3 months for 24 months (in Part B). The follow-up will be performed by telephone contact or (e)mail.

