6.1.9. End of Treatment Visit

Time-point: 2 weeks after the last CTL-002 infusion (\pm 2 days)

- Vital signs
- AEs
- Concomitant medications
- Physical examination (including neurological examination [check for motor neuropathy])

- ECOG Performance Status
- Weight assessment
- SARS-CoV-2 (COVID-19) testing (RNA and antibody testing)
- Safety laboratory testing (hematology, clinical chemistry, coagulation)
- Assessment of thyroid hormones, HbA1c, and NT-proBNP
- Safety urine analysis
- Urine analysis of GDF-15 (Part A only)
- Urine pregnancy test (if positive, confirm with serum test)
- Immune monitoring (cytokines/chemokines)
- PK
- Serum analysis of GDF-15
- Immunogenicity/ADA testing
- Blood molecular/transcriptional profiling (Part A only)
- Infectious diseases/serology
- Immunoglobulins
- Tumor assessment/Imaging: CT/MRI/PET-Scan to document tumor burden according to RECIST/iRECIST (Refer to [Appendix 2](#)): End of Treatment Visit only if last scan is more than 4 weeks old
- L3SMI (only if last scan is more than 4 weeks old) (Part A only)
- MCASCO (Part A only)
- Cutaneous tumor lesion assessment/photography
- ECG
- Echocardiography or MUGA if ECHO cannot be performed

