6.1.10. Safety Follow-up Visit

Time-point: 30 days post last infusion (± 2 days)

- Vital signs
- AEs
- Concomitant medications
- Safety laboratory testing (hematology, clinical chemistry, coagulation)
- Urine pregnancy test (if positive, to be confirmed with serum test)
- Physical examination (including neurological examination [check for motor neuropathy])
- ECOG Performance Status

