8.3.3. Efficacy Analysis

Efficacy analyses will be based on the Efficacy Evaluable Analysis Set and will include summaries of confirmed PR/CR, ORR, DoR, PFS, TTR, and OS by dose level (Part A) or cohort (Part B). Tumor response will be evaluated according to institutional standards using RECIST V1.1 for solid tumors, as well as iRECIST criteria. The definitions of the response evaluation endpoints are as follows:

Table 10 Definitions of Response Evaluation (RECIST V1.1)

Duration of Response:	Duration of response will be measured from the time that measurement criteria are met for CR or PR (whichever status is recorded first) until the first date that PD or death is documented. This analysis will include subjects with overall best response being CR or PR only. Subjects who neither progressed nor died will be censored at the date of the last tumor assessment
Overall Response Rate	Overall response rate is defined as the percentage of subjects with a CR or PR as assessed by RECIST V1.1. A responder is defined as a subject experiencing either a CR or PR by these criteria. Subjects with no tumor assessment after the start of study treatment are to be considered as non-responders.
Progression Free Survival	Progression-free survival is defined as the length of time between first study drug administration and the date of the first occurrence of disease progression or death from any cause.
Time to Response	Time to response will be measured from the time of first study administration until the day of documented CR or PR (whichever status is recorded first). Subjects without response will be censored at the date of the last tumor assessment or the date of death.
Overall Survival	Overall survival is defined as the time from the study drug administration to the date of death, regardless of the cause of death. Subjects who were alive at the time of the analysis will be censored at the date the subject was last known to be alive. Subjects without follow-up assessment will be censored at the day of their last dose and subjects with no post-baseline information will be censored at the time of their first study drug administration.

Abbreviations: CR = complete response; PD = progressive disease; PR = partial response; RECIST = Response Evaluation Criteria in Solid Tumors

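### Table 10's last-dose censoring clause for overall survival conflicts with its last-known-alive rule, unless the undefined term 'follow-up assessment' makes the clause redundant

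*Protocol*

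**What the plan says.** Table 10 (Protocol, Section 8.3.3) defines the event without any time limit relative to dosing: "Overall survival is defined as the time from the study drug administration to the date of death, regardless of the cause of death". Three censoring rules follow:

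- The general rule: "Subjects who were alive at the time of the analysis will be censored at the date the subject was last known to be alive".
- The rule at issue: "Subjects without follow-up assessment will be censored at the day of their last dose".
- A rule for those without data: "subjects with no post-baseline information will be censored at the time of their first study drug administration".

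Two contacts after the last dose are scheduled within the core study. The End of Treatment Visit is "2 weeks after the last CTL-002 infusion" (Section 6.1.9) and the Safety Follow-up Visit is "30 days post last infusion" (Section 6.1.10). The survival phase starts only after that: "Following the Safety Follow-up Visit / End of Core Study Visit, subjects will be followed up with an Efficacy and Survival follow-up" (Section 2.4). Its contacts are every 3 months (Section 6.1.11).

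**The concern.** Because subjects with no data after baseline have their own rule, the last-dose rule must apply to subjects who do have such data. Some of them will have been examined alive after the last dose. On the narrow reading of 'follow-up assessment', the general rule censors such a subject at the day-30 visit and the next rule censors the same subject at day 0. Both cannot apply.

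The error runs in one direction. Survivors leave the risk set at last dose, while deaths over the same days still count. OS is listed among the Part B primary endpoints (Section 1.10.1) and the study is single-arm (Section 5.7), so no control group carries the same error. The rule also reaches beyond subjects who are lost. In a summary produced during the study, which Section 8.4 allows, a subject past the safety visit but not yet at the first 3-monthly contact has no survival follow-up either.

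**Working it through.** **No figure to reproduce.** The protocol states no assumed OS median, event count or loss rate. The check therefore concerns meaning, direction and size.

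**Step 1: meaning of the term.** Three readings are possible:

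| 'Follow-up assessment' means | Who is censored at last dose | Known survival lost |
|---|---|---|
| Efficacy and Survival follow-up (6.1.11) | Seen at 2 weeks or 30 days, not contacted later | Up to about 30 days |
| Safety Follow-up Visit or later | Seen at 2 weeks only | Up to about 14 days |
| Any contact after last dose | Not seen after last dose | None; clause redundant |

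Section 2.4 supports the first reading. So does Section 3.3, which names the End of Treatment Visit (6.1.9) and the follow-up (6.1.11) as separate things. The name of the Safety Follow-up Visit supports the second. Generic uses of 'follow-up' for post-baseline imaging in Section 6.2.5.1 and Appendix 1 point to a broader sense.

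**Step 2: direction, by a small example.** Fourteen subjects share a last-dose day. One dies 20 days later, and four are seen alive at day 30 and never again. The Kaplan-Meier factor at the death is 1 - d/n:

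- Last known alive: n = 14, so 1 - 1/14 = 0.929.
- Last dose: n = 14 - 4 = 10, so 1 - 1/10 = 0.900.

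Deaths in this window are captured. Serious events are collected to 30 days after treatment (Section 7.1.1), deaths from progression go on a separate eCRF form (Section 7.2.5), and deaths are listed for all subjects (Section 8.3.2).

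**Step 3: size under the first reading.** This was a Kaplan-Meier simulation with 400,000 subjects in each of 18 scenarios.

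- From the protocol: 14-day dosing grid; last scheduled visit 30 days after last dose.
- Assumed: exponential OS with median 6, 9 or 12 months; exponential time on treatment with median 2 or 4 months; administrative cut between 12 and 24 months; 10%, 20% or 30% of subjects never entering survival follow-up, at random.

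Range of the drop in median OS, last-dose against last-known-alive censoring:

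| No survival follow-up | Drop in median (months) |
|---|---|
| 10% | 0.06-0.10 |
| 20% | 0.12-0.22 |
| 30% | 0.19-0.35 |

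The largest relative drop is at a true median of 6 months, 2 months on treatment and 30% without follow-up: (6.00 - 5.71)/6.00 = 4.8%. Among the smallest is a true median of 12 months, 4 months on treatment and 10%: (11.99 - 11.90)/11.99 = 0.8%. Survival at 12 months falls by 0.2 to 1.0 percentage points. Between 5.5% and about 25% of all subjects are affected, each losing about 30 days. Censoring at last known alive recovers the true median to within 0.03 months throughout.

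**Step 4: size against sampling error.** Under exponential OS without earlier censoring, SE(median) = (0.5/√n)/(0.5λ) = 1/(λ√n). The median is ln 2/λ, so the relative SE is 1/(ln 2·√n) = 1.44/√n:

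- n = 14: 39%
- n = 27: 28%
- n = 75: 17%

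The largest shift, 4.8%, is 4.8/28 ≈ 0.17 SE at n = 27 and 4.8/17 ≈ 0.28 SE at n = 75.

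**The case against.** The strongest reply is that Table 10 can be read as a fallback sequence: last known alive; if nothing after dosing, last dose; if nothing after baseline, first dose. A subject seen at day 30 then falls under the first rule, and nothing is contradicted or lost. Since the term is undefined, this reading cannot be excluded, and the bias has to be stated conditionally. That stands. It does not save the clause, because on the fallback reading the clause adds nothing to the rule before it.

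It is also fair that the size rests on assumption. Survival contact is by telephone or (e)mail, and the protocol gives no ground for expecting 20-30% never to be reached. The study is described as explorative without formal comparisons (Section 8.1), and cohort expansion depends on responder counts. No stated rule uses OS.

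A reader might infer two stronger points, and the documents support neither:

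- That up to 12 weeks of survival are lost for a subject on a treatment hold. The 12 weeks in Table 4 generally run from the start of steroids and limit resolution or taper before permanent discontinuation; they do not describe a dosing gap at a data cut. Section 8.4 plans no formal interim analysis, and under Section 9.5 the study ends 24 months after the Part B core study, when dosing is over.
- That the error distorts comparisons between cohorts for non-clinical reasons. The protocol gives no loss rate by cohort and plans no such comparison.

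**Conclusion.** The concern holds as a small correction to a stated rule. Two sentences of Table 10 conflict if 'follow-up assessment' means the 3-monthly survival phase, which is the sense that Sections 2.4 and 3.3 suggest. On that reading Kaplan-Meier OS is biased downward, by roughly 1-5% of the median if 10-30% of subjects lack survival follow-up. Those rates, the exponential survival and treatment times, and loss at random are assumptions. On the second reading the loss is at most about 14 days per affected subject; that case was not simulated. On the third there is no effect. It would go too far to say that OS in this trial will be biased, or that a conclusion would change: the term is open, and the shift is well under one standard error for the cohort sizes planned. On no reading does the clause improve the estimate.

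**What to change.** Delete the last-dose clause from the OS row of Table 10 and state one rule, for example: *Anyone not known to have died is censored on the last date known alive, counting the End of Treatment and Safety Follow-up Visits; anyone with no data after baseline is censored on the date of first study drug administration.*

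The cost is one sentence. Both visits are already in the schedules of assessments, so no new data, visit or clinical procedure is needed. If the sponsor prefers to keep the clause, the minimum is to define 'follow-up assessment' as any contact after the last dose, which brings the clause into line with the general rule.

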8.3.4. Pharmacokinetic Analysis

Plasma concentrations of CTL-002 will be summarized by dose level (Part A) and cohort (Part B) using descriptive statistics (number of subjects [n], mean, standard deviation, coefficient of variation (CV%), geometric mean, geometric CV%, median, minimum, and maximum by nominal time point. Summary statistics will also be provided for PK parameters by cycle, including but not limited to AUC, C_{max} , and $t_{1/2}$.

8.3.5. Pharmacodynamic and Exploratory Analyses

Pharmacodynamic effects will be based on appropriate summaries of cytokines, chemokines, and other circulating biomarkers (see [Section 6.2.4.8](#)). Correlations of GDF-15 serum levels with certain pharmacodynamic results may be included graphically.

Exploratory endpoints will be based on summaries of immune cell phenotyping, molecular profiling and iRECIST parameters (see [Section 6.2.4.9](#))

Note: Not all subject samples will be analyzed under “exploratory research/endpoints.” The decision to analyze certain samples will be based on emerging data, data that indicates specific tumor indications and/or subjects where CTL-002 administered as monotherapy and/or in combination with a PD-1/PD-L1 inhibitor demonstrates increased tumor immune cell infiltration.

8.4. Interim Analysis

No formal interim data analysis is planned. However, the Sponsor will review Part A data produced, and based on safety, pharmaco-modelling data, and response data (as far as available), define an initial recommended dose for Part B (Phase 2a; expansion) and to support the submission of the substantial amendment to competent authorities and IEC/IRB. Other summaries of the data may be provided at any point during the study and used to help the Safety Review Committee and the Sponsor make informed decisions.

8.5. Sample Size

The sample size for Part A (Phase 1; dose escalation) of the study is not based on any statistical assumptions; rather, it follows the classic ‘3+3 rule,’ a well-established methodology in the design of dose-finding clinical trials in oncology.

The study plans for up to 5 dose escalation cohorts in Part A, with each cohort comprising a minimum of 3 subjects to be treated with CTL-002 in combination with the defined checkpoint inhibitor at each dose escalating level and with typical DLT driven expansions up to 6 subjects per cohort and at the MTD.

For Part A of the study (Phase 1; dose escalation), it is anticipated that a minimum of 24 subjects will be enrolled.

For Part B of the study (Phase 2a; expansion), up to 249 subjects will be enrolled in different expansion cohorts (79 response evaluable subjects in the first cohorts, with expansion option of 4×13, 1×24 and 1×19 subjects = 95 subjects, and 75 subjects in the biomarker cohort with mixed solid tumors; “basket” cohort). Therefore, a total of approximately 274 subjects might be enrolled (Part A: n = 25 / Part B: n = 79 + 95 + 75 = 249). Additional cohorts may be added via substantial amendment, only.

8.6. Level of Significance

The level of significance, alpha (α), for this trial is 0.05.

8.7. Criteria for the Termination of the Study

No statistical stopping rules will be formulated for this study.

8.8. Procedure for Accounting for Missing, Unused and Spurious Data

Missing, unused and spurious data will be dealt with as such. There is no intention to implement any procedure for replacing missing data.

8.9. Deviations from the Original Planned Analysis

Planned statistical analyses will be documented in the final SAP before database lock. Any changes to the planned statistical methods will be documented in the clinical study report.

9. SUPPORTING DOCUMENTATION AND OPERATIONAL CONSIDERATIONS

9.1. Regulatory, Ethical and Study Oversight Considerations

9.1.1. Ethical Conduct of the Study

The study will be performed in accordance with ethical principles that have their origin in the Declaration of Helsinki and are consistent with the ICH/GCP guidelines, applicable regulatory requirements and the Sponsor or delegated representatives' policy on Bioethics and Human Biological Samples.

9.1.2. Ethics and Regulatory Review

The study will not be initiated without approval of the national Competent Authority and appropriate IEC/IRB and compliance with all administrative requirements of the governing body of the institution.

This will include approval of the exploratory biomarker and pharmacogenetic research and associated consent(s) forms. The Investigator will ensure the distribution of these documents to the applicable IEC/IRB, and to the trial site staff.

The Sponsor or designated representative will provide Regulatory Authorities, IECs, and PIs with safety updates/reports according to local requirements, including Suspected Unexpected Serious Adverse Reactions (SUSARs), where relevant.

Each Principal Investigator is responsible for providing the IEC/IRB with reports of any serious and unexpected adverse drug reactions from any other study conducted with the investigational product. The Sponsor or designated representative will provide this information to the PI so that he/she can meet these reporting requirements.

9.2. Ethics/Independent Ethics Committee /Institutional Review Board /

The Principal Investigator (PI) must obtain IEC/IRB approval for the investigation. Initial IEC/IRB approval, and all materials approved by the IEC/IRB for this study including the subject ICF and recruitment materials (if applicable) must be maintained by the Investigator and made available for inspection.

The PI must submit written approval to the Sponsor or its representative before he or she can enroll any subject into the study.

The PI is responsible for informing the IEC of any amendment to the protocol in accordance with local requirements. In addition, the IEC/IRB must approve all advertising that may be used to recruit subjects for the study. The protocol must be re-approved by the IEC/IRB upon receipt of amendments and annually, as local regulations require.

The PI is also responsible for providing the IEC/IRB with reports of any reportable serious adverse drug reactions from any other study conducted with the investigational product. The Sponsor or its representative will provide this information to the PI.

Progress reports and notifications of serious adverse drug reactions will be provided to the IEC/IRB according to local regulations and guidelines.

The study will be performed in accordance with ethical principles that have their origin in the Declaration of Helsinki (See [Appendix 5](#)) and are consistent with ICH/GCP, applicable regulatory requirements and the Sponsors policy on Bioethics.

9.3. Informed Consent

The PI at each center will ensure that the subject is given full and adequate oral and written information about the nature, purpose, possible risk and benefit of the study. Subjects must also be notified that they are free to discontinue from the study at any time. The subject should be given the opportunity to ask questions and allowed time to consider the information provided.

The subjects signed and dated informed consent must be obtained before conducting any study procedures.

The PI(s) must maintain the original, signed ICF. A copy of the signed ICF must be given to the subject.

The Investigator will obtain written informed consent from each subject participating in the study:

- Ensure that each subject is given full and adequate oral and written information about the nature, purpose, possible risk and benefit of the study and the exploratory biomarker assessments
- Ensure that each subject is notified that they are free to withdraw from the study or the subsequent biomarker assessments at any time
- Ensure that each subject is given the opportunity to ask questions and allowed time to consider the information provided and discuss the study with their family or surrogates
- Ensure each subject provides signed and dated informed consent before conducting any procedure specifically for the study
- Ensure each original, signed ICF is stored in the Investigator's Study File/medical records
- Ensure a copy of each signed ICF is given to the subject

9.3.1. Changes to the Protocol and Informed Consent Form

No modification of the protocol should be implemented without the prior written approval of the Sponsor or the Sponsor's representative.

Any such changes which may affect a subject's treatment or informed consent, especially those increasing potential risks, must receive prior approval by the IEC/IRB and the concerned Competent Authorities. The exception to this is where modifications are necessary to eliminate an immediate hazard to trial subjects, or when the change involves only logistical or administrative aspects of the trial (e.g., change in monitor, change in telephone number).

Other administrative revisions which may impact the clinical portion of a study will be duly reported to the IEC/IRB by the Principal Investigator.

9.4. Subject Confidentiality

Subject confidentiality and privacy are strictly held in trust by the participating investigators, their staff, and the Sponsor(s) and their interventions as per local regulations. This confidentiality is extended to cover testing of biological samples and genetic tests in addition to the clinical information relating to subjects. Therefore, the study protocol, documentation, data, and all other information generated will be held in strict confidence. No information concerning the study, or the data will be released to any unauthorized third party without prior written approval of the Sponsor.

All research activities will be conducted in as private a setting as possible.

The study monitor, other authorized representatives of the Sponsor, representatives of the IEC/IRB, regulatory agencies or pharmaceutical company supplying study product may inspect all documents and records required to be maintained by the Investigator, including but not limited to, medical records (office, clinic, or hospital) and pharmacy records for the subjects in this study. The clinical trial site will permit access to such records.

The study subject's contact information will be securely stored at each trial site for internal use during the study. At the end of the study, all records will continue to be kept in a secure location for as long a period as dictated by the reviewing IEC/IRB, Institutional policies, or Sponsor requirements.

Subject research data, which is for purposes of statistical analysis and scientific reporting, will be transmitted to and stored at the designated Clinical Research Organization supporting the study. This will not include the subject's contact or identifying information. Rather, individual subjects and their research data will be identified by a unique study identification number. The study data entry and study management systems used by clinical sites and by the designated Clinical Research Organization's research staff will be secured, and password protected. At the end of the study, all study databases will be de-identified and archived by the designated Clinical Research Organization.

9.5. Study Termination

Although Sponsor has every intention of completing the study, it reserves the right to discontinue the study at any time for clinical or administrative reasons.

The end of the core study is defined as the time point when the last subject has completed the last Safety Follow-up Visit (End of Core Study Visit) 30 days from the last dose.

The end of study is defined as the time point when the last subject has completed the last Efficacy and Survival follow-up. This is 12 months after end of the core study for Part A and 24 months after end of the core study for Part B.

